12.3 Prohibited Medications/Therapies

Prior to discontinuation of tagraxofusp, patients may not receive the following anticancer/antimyeloproliferative agents: JAKi (ruxolitinib, fadaratinib, and others), interferon- α , thalidomide, lenalidomide, cytotoxic chemotherapy agents (including 2-chlorodeoxyadenosine and other purine analogs), hypomethylating agents (5-aza, decitabine and others), tyrosine kinase inhibitors (including those which inhibit the BCR-ABL kinase such as imatinib), HU, and investigational anti-cancer agents.

Patients may not receive additional disease-modifying or cytoreductive agents such as danazol or anagrelide. Patients may not receive erythroid- or platelet-stimulating growth factors.

Hydroxyurea is prohibited during study participation except for cycle 1; Short-term treatment with HU beyond cycle 1 with approval of the Medical Monitor is permitted.

Ongoing corticosteroid therapy at doses of > 20 mg/day prednisone (or equivalent) for > 7 days is not permitted; however transient increases in corticosteroid doses in the setting of infections or other “stress” settings are allowed.

13 Adverse Events and Safety Evaluation

The AE reporting period for a patient treated in the study begins with provision of consent and is continuous through 30 days after the last tagraxofusp infusion. All AEs that occur in treated patients during the AE reporting period must be reported to the Sponsor or designee, whether or not the event is considered related to tagraxofusp. Any known untoward event that occurs beyond the AE reporting period (30 days after the last tagraxofusp infusion) that the Investigator assesses as related to tagraxofusp should also be reported as an AE.

All patients should be monitored for at least 1 hour (or longer at the Investigator’s discretion) following the administration of each tagraxofusp infusion. The Investigator or designated medical staff responsible for study conduct and safety evaluations, should be available during the administration of tagraxofusp and follow-up to assess, treat, or report as necessary any AE or SAE that may occur.

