3.10. Missing, Unused, and Spurious Data

In general, there will be no substitutions made to accommodate missing data points. All data recorded on the eCRF will be included in data listings that will accompany the CSR.

For categorical variables, a category for missing data of the parameter will be presented. Percentages will be calculated from the total population, including patients with missing results.

When tabulating AE data, partial dates will be handled as follows. If the day of the month is missing, the onset day will be set to the first day of the month unless it is the same month and year as study treatment. In this case, in order to conservatively report the event as treatment-emergent, the onset date will be assumed to be the date of treatment. If the onset day and month are both missing, the day and month will be assumed to be January 1, unless the event occurred in the same year as the study treatment. In this case, the event onset will be coded to the day of

treatment in order to conservatively report the event as treatment-emergent. A missing onset date will be set up to the first day of treatment.

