4.4.2. Adverse Events

All AEs will be coded using the MedDRA coding system version 19.0 and displayed in tables and data listings using system organ class (SOC) and preferred term (PT) based on Safety Population.

Analyses of AEs will be performed for those events that are considered treatment-emergent, where treatment-emergent is defined per protocol as any AE with onset after the first administration of tagraxofusp through 30 days after the last dose of tagraxofusp, or any event that was present at baseline but worsened in intensity or was subsequently considered drug-related by the Investigator through 30 days after the last dose of tagraxofusp.

Tabulations of the number and percentage of patients with any treatment-emergent AE (TEAE), common AEs (defined as occurring in $\geq 10\%$ of the study sample [overall for summaries by dose, within each disease for summaries by disease]), with any TEAE assessed by the Investigator as related to treatment, with any TEAE with severity \geq Common Terminology Criteria for Adverse Events (CTCAE) Grade 3, with any serious adverse event (SAE), with any AE leading to discontinuation of study treatment, with any AE to dose reduction, with any AE leading to dose interruption, with any AE leading to death, with any AE leading to death within 30 days, and with any AE leading to death within 60 days will be summarized as described in [Section 3.5](#). An overall summary of the incidence of TEAEs will also be provided.

In these tabulations, each patient will contribute only once (ie, the most related occurrence or the most intense occurrence) to each of the incidence rates in the descriptive analysis, regardless of the number of episodes. Treatment-emergent AEs (TEAEs) are summarized by patient incidence rates; therefore, in such tabulations, a patient contributes only once to the count for a given SOC or PT. For tabulations that include classification by relationship to study treatment, AEs with missing relationship will be considered related to study drug.

By-patient tabulations will also be presented for patients who died, SAEs, AEs leading to study drug discontinuation, AEs with CTCAE Grade 3, and AEs with CTCAE Grade 4.

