4.4.2.1. Capillary Leak Syndrome

In addition to the summaries described in [Section 4.4.2](#), summaries will be provided that include:

- Summary of number of CLS events, number of CLS events by CTCAE Grade, and time to first onset and time to resolution of CLS events;
- Summary incidence of albumin infusions and timing of infusions in relation to CLS onset;
- Summary incidence of steroids used
- Summary incidence of recurring CLS
- Summaries of CLS leading to treatment discontinuation, dose reduction, and dose interruption

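### The AE partial-date rule in SAP 3.10 does not check the stop date, so an event recorded as ended before the first infusion can be tabulated as treatment-emergent

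*SAP*

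**What the plan says.** SAP 3.10 starts from a general policy of not substituting for missing data, then makes an exception for AE onset dates. The exception has three branches that move onset to the treatment date:

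- **Day missing.** "the onset day will be set to the first day of the month unless it is the same month and year as study treatment". For the same-month case: "In this case, in order to conservatively report the event as treatment-emergent, the onset date will be assumed to be the date of treatment".
- **Day and month missing, same year as treatment.** Onset is coded to the day of "treatment in order to conservatively report the event as treatment-emergent".
- **Whole date missing.** "A missing onset date will be set up to the first day of treatment".

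SAP 4.4.2 defines a treatment-emergent event as "any AE with onset after the first administration of tagraxofusp through 30 days after the last dose of tagraxofusp", and adds events present at baseline that later worsen or are later judged drug-related.

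On collection, Protocol 13 says: "The AE reporting period for a patient treated in the study begins with provision of consent". Sections 13.2 and 13.5 repeat this, and the Stage 3A schedule (Protocol Table 4) marks AE monitoring at screening, Day -28 to 0.

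Neither SAP 3.10 nor the treatment-emergent definition mentions the AE stop date. The SAP does have an end-date rule in 4.4.6, but only for concomitant medications: those stopped before the first dose are left out, and a missing or ongoing end date leads to inclusion.

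**The concern.** Imputing towards the treatment date is sensible when nobody can tell whether an event began before or after dosing. The reason the SAP gives, conservative reporting, fits that case. It does not fit an event whose recorded stop date precedes the first infusion. That event cannot have started on treatment, whatever day is missing from its onset. The rule then overrides collected information and produces an impossible date order.

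At stake is the accuracy of the treatment-emergent tables. An event from screening would appear under its preferred term as occurring on tagraxofusp, and in the by-cycle summary as a Cycle 1 onset.

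A smaller wording problem sits in the same rule. It speaks variously of study treatment, the date of treatment and the first day of treatment. Dosing recurs every 21 or 28 days, so the same-month test should say which treatment date it means.

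**Working it through.** The plan gives no figure to reproduce, so the check applies the rule literally.

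**Inputs.** The three branches of SAP 3.10; the onset-based definition in SAP 4.4.2; the 28-day screening window in Protocol Table 4. The calendar dates below are assumed for illustration. Onset on the day of first infusion is treated as treatment-emergent. SAP 4.4.2 says after the first administration, but counting such events is the rule's stated purpose.

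**Worked cases, first infusion 20 June 2020**

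| Recorded onset | Recorded stop | Imputed onset | Treatment-emergent? | Onset after stop? |
|---|---|---|---|---|
| June 2020, day missing | 10 June | 20 June | Yes | Yes, by 20 - 10 = 10 days |
| 2020, day and month missing | 10 June | 20 June | Yes | Yes, by 10 days |
| Fully missing | 10 June | 20 June | Yes | Yes, by 10 days |
| May 2020, day missing | 10 June | 1 May | No | No |
| 5 June 2020, complete | 10 June | not imputed | No | No |
| June 2020, day missing | 25 June | 20 June | Yes | No |
| June 2020, day missing | ongoing | 20 June | Yes | Not applicable |

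The first three rows are wrong. The last two are the cases the rule was written for, and it handles them as intended.

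**How often each branch fails, given such a record.** Take every onset/stop pair lying 1 to 28 days before the first infusion, with stop on or after onset: 28 × 29 / 2 = 406 pairs. Repeat for each first-infusion date in 2020: 406 × 366 = 148,596 combinations, equally weighted (an assumption). The rule gives treatment-emergent status with onset after stop in:

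- 37.7% when the day is missing (it fails only if onset falls in the same calendar month as the first infusion);
- 94.8% when day and month are missing (it fails only if onset falls in the same year);
- 100% when the date is fully missing, which is true by construction.

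These percentages are conditional on an event that resolved before dosing having that type of incomplete onset. They are not estimates of how many AEs are affected.

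**Effect per patient.** At the planned cohort size of about 20 (SAP 3.1.2), one misclassified patient adds 1/20 = 5 percentage points to a preferred term.

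**Check of the remedy.** If imputation to the first infusion is allowed only when the stop date is missing, ongoing, or on or after that infusion, the first three rows are no longer treatment-emergent. The last two stay treatment-emergent with onset 20 June.

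**The case against.** The case against giving this much weight is good, and most of it stands.

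- **The trigger is narrow.** The event must start after consent, end before the first infusion, lack a full onset date, and still have a usable stop date. Protocol 16.12 has the monitor and data manager query missing or spurious data, which should catch some of these records. SAP 3.10 also lists all eCRF data, so the recorded dates remain visible.
- **Little pre-treatment disease can enter.** Conditions before consent go to medical history (Protocol 13.2). Pre-existing conditions count as AEs only if they worsen by at least one CTCAE grade (13.3). A reader might infer that background CMML morbidity would be widely reported as drug toxicity; these provisions do not support that.
- **Capillary leak timing.** SAP 4.4.2.1 plans summaries of "time to first onset and time to resolution of CLS events", and a reader might infer that these would come out negative. Protocol 8.2.3.1 ties the syndrome to drug administration, 3 to 8 days after starting treatment, so a case resolved before dosing is not credible. The special-interest grouping also includes low albumin and proteinuria terms, so a screening laboratory event could in theory enter. Nothing in the documents makes that likely, and no other AE-duration analysis is planned.
- **Relatedness.** SAP 4.4.2 treats missing causality as related, but Protocol 13.6 requires an investigator determination for every AE. A misdated event also counted as related would need a second rare coincidence.
- **Direction.** The error only adds treatment-emergent events. The study is non-randomized, the analyses are descriptive (SAP 5), and no Type I error control applies (SAP 3.7).

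None of this supplies the missing check. A programmer might add one unprompted, but the SAP as written instructs the opposite.

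**Conclusion.** The point holds as a low-priority correction. In all three branches, SAP 3.10 gives a wrong classification for an AE with an incomplete onset and a recorded stop before the first infusion. This is a stated rule with a wrong result, not merely an omitted detail.

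The number of such records cannot be learned from the documents. That it is small is a judgement based on the short screening window and the query process. The bias runs one way, towards too many treatment-emergent events, and hides no harm. The 5-point figure rests on the planned cohort of 20. SAP 5 says Stage 3A enrollment was not continued, so a smaller cohort would raise the per-patient effect, while the pooled columns in SAP 3.5 would lower it. The documents do not support a claim that the overall safety profile is materially distorted.

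**What to change.** Add to SAP 3.10:

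- A partial or missing AE onset is imputed to the date of the first infusion only if the stop date is missing, the event is ongoing, or the stop date is on or after the first infusion. A partial stop date that could still fall on or after the first infusion is treated the same way.
- If the known stop date, or its month and year, is before the first infusion, the event is not treatment-emergent, and any imputed onset may not be later than the stop date.
- Use *first infusion* in place of *study treatment* and its variants throughout the rule.

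This brings AEs into line with the end-date logic already used for concomitant medications in SAP 4.4.6. The cost is one or two sentences and one programming condition. The downside is slightly fewer events counted as treatment-emergent, all with a documented end before dosing. Events of genuinely uncertain timing are still handled conservatively.

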3.11. Visit Windows

It is expected that all visits should occur according to the protocol schedule. All data will be tabulated per the evaluation visit as recorded on the eCRF even if the assessment is outside of the visit window. In data listings, the relative day of all dates will be presented (see [Section 3.2](#)).

3.12. Timing of Analyses

[REDACTED]

Efficacy data were not summarized at that time. The respective analyses were described in a separate Statistical Analysis Plan.

The final, end of study, analyses after database lock in support of the CSR will be supported from the analyses described in this document. Ongoing survival follow-up will be described in the CSR.

4. STUDY ANALYSES

4.1. Patient Disposition

Patient disposition will be tabulated as described in [Section 3.5](#) and include the number screened, the number treated in total, the number in each patient population for analysis, the number who withdrew prior to completing treatment and reason(s) for withdrawal, and the number who withdrew prior to completing the study and reason(s) for withdrawal. The number of patients who received stem cell transplant since discontinuation will also be reported.

A data listing of study completion information including the reason for premature study withdrawal, if applicable, will be presented. A data listing of patient populations will also be presented.

4.2. Demographics and Baseline Characteristics

Demographics and baseline characteristics will be summarized as described in [Section 3.5](#). Age, height, and weight will be summarized using descriptive statistics (number of patients, mean, SD, median, minimum, and maximum). The number and percentage of patients in each gender, race, ethnicity, and ECOG PS categories also will be presented.

Primary disease history will be summarized for MF and CMML. MF disease history will include DIPSS-plus score risk factors and profile, type of MF (primary, post polycythemia, post essential thrombocythemia), type of abnormal karyotype, mutation status, and time since diagnosis. CMML disease history will include diagnosis criteria, CMML type (CMML-1 or CMML-2), symptoms, cytogenetic risk profile, monocytic cell nodules in bone marrow biopsy (yes/no), mutations, prognostic scoring system molecular risk profile, and time since diagnosis. Baseline laboratory data, including monocytes, platelets, hemoglobin, white blood cell, lactate dehydrogenase, bone marrow blasts, peripheral blood blasts, will be summarized for all patients. Additionally, baseline MPN-SAF TSS, transfusion dependence status (yes/no) for red blood cells and platelets, spleen size by MRI/CT and by Physical Exam, the presence of splenomegaly at baseline (yes/no), and the presence of hepatomegaly at baseline (yes/no) will be summarized for all patients. SM disease history will be included in a data listing and will include diagnosis criteria, mutations, and molecular markers..

Receipt (yes/no) of prior systemic therapy, prior radiation therapy, and prior stem cell transplant (SCT) will be summarized. The number and type of prior systemic therapy for MPN will be presented. The reason why the patient was not considered an immediate candidate for SCT will also be summarized.

All analyses of demographic/baseline data will be performed using the Safety Population and select analyses will be repeated using the mITT Population.

Demographic, baseline, medical history, and disease history data for each patient will be provided in data listings.

4.3. Efficacy Evaluation

Efficacy analyses will be conducted using the mITT population for patients treated at 12 µg/kg/day. Supportive analysis of efficacy based on the Safety Population will be performed for patients treated at 12 µg/kg/day and patients treated at 7 or 9 µg/kg/day. Efficacy summaries will be presented as described in [Section 3.5](#). Data for all efficacy endpoints will be presented in by-patient listings.

4.3.1. Response Rate

Objective response rate and the corresponding 95% Clopper Exact CIs will be presented as the number and percentage of patients who achieve disease-specific complete response (CR) or partial response (PR) after treatment.

Best overall response will be presented as the number and percentage of patients who achieve disease-specific (see [Section 8](#)) CR, PR, stable disease (SD), progressive disease (PD) or who are not evaluable (NE) as their best response on study.

Swim lane plots will be produced for each disease presenting the time on treatment and in response.

The time from the date of first infusion of tagraxofusp to the date from when criteria are first met for CR or PR will be summarized.

Patients who remain in response per investigator and receive a stem cell transplant will be identified and summarized.

For MF patients, the number and percentage of patients who achieved clinical improvement, anemia, spleen, or symptom responses, molecular remission, or cytogenetic/molecular relapse will also be presented using IWG-MRT/ELN criteria (see [Section 8.1](#) for disease specific response criteria). The time from date of first infusion of tagraxofusp to the date from when each response of clinical benefit criteria (as defined in Table 8-4 in [Section 8.2](#)) are first met will be summarized.

For CMML patients, the number and percentage of patients who achieved erythroid, platelet, neutrophil, spleen or symptoms responses will also be presented (see [Section 8.2](#) for disease specific response criteria). The time from date of first infusion of tagraxofusp to the date from when each category of clinical benefit criteria are first met will be summarized.

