The hematology community has recognized that a lack of a stable disease category in the 2015 MDS/MPN IWG criteria creates considerable uncertainty in the categorization of patients on any CMML study. Therefore, the stable disease category defined as those patients not belonging to any of the defined categories in the 2015 criteria has been added as response criteria for CMML patients.

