1.1.3.3. Stage 3A Study Objectives

Objectives of Stage 3A in patients with CMML are:

- To characterize the safety profile of tagraxofusp.
- To obtain preliminary evidence of response to tagraxofusp therapy as assessed by the MDS/MPN 2015 criteria ([Savona 2015](#)), with the addition of a stable disease (SD) category, and to obtain data relative to additional clinical parameters that may be used in determination of therapeutic benefit.

The MDS/MPN 2015 criteria ([Savona 2015](#)) represent the current consensus criteria for evaluation of clinical benefit in patients with CMML, beyond those specified in the IWG-MDS criteria ([Cheson 2006](#)). Thus, as an inherent component of the design of Stage 3A, responses to treatment are being assessed using the MDS/MPN 2015 criteria. The hematology community has recognized that a lack of a SD category in the 2015 MDS/MPN IWG criteria creates

considerable uncertainty in the categorization of patients on any CMML study. Therefore, a SD category, defined as those patients not belonging to any of the defined categories in the 2015 criteria, has been added as a response category.

The purpose of Stage 3A, is to analytically evaluate the clinical benefit derived from individual components, or variations thereof, of the MDS/MPN 2015 criteria that may allow for a prospective definition of a primary efficacy endpoint. Clinical benefit includes erythroid, platelet, neutrophil, spleen, and symptom responses, as defined in Table 8-4 in [Section 8.2](#), as well as transfusion dependence status and symptom score.

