4.3.2. Duration of Response

Duration of objective response is defined as the time from when the disease specific criteria (see [Section 8](#)) are first met for CR or PR until the date that the criteria for relapse (including SD, progressive disease [PD], or relapse) after CR/PR is met, or death. In the case that SD follows CR/PR and there is no evidence that response rebounds to CR/PR, duration of objective response will end at the time of first reduction of response to below CR/PR. For patients who receive SCT after CR/PR, DOR will include time to disease relapse post-transplant. Patients who are lost to follow-up or who do not relapse after objective response as of the analysis date will be censored on the latter of the date of last treatment with tagraxofusp or date of last disease

assessment recorded prior to the analysis date. If patient starts other anticancer therapies (with the exception of SCT), they will be censored at the latter of the date of last treatment with tagraxofusp or date of last disease assessment recorded that occurred prior to the start of the new therapy.

The distribution of DOR will be estimated by Kaplan-Meier methodology and the 25th percentile, median, and 75th percentile of time to event, number and percentage of events and censored observations, and appropriate 95% CIs will be presented.

For MF patients, the median duration of response for each category of clinical benefit, including clinical improvement, anemia, spleen, or symptom responses, molecular remission, or cytogenetic/molecular relapse, will be derived similar to the duration of objective response. For CMML patients, the median duration of response for each category of clinical benefit, including erythroid, platelet, neutrophil, spleen or symptoms responses, will be derived similar to the duration of objective response.

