8. RESPONSE CRITERIA

8.1. Myelofibrosis

Table 8-1 Stage 2: Revised IWG-MRT and ELN Response Criteria for MF

Response categories	Required criteria (for all response categories, benefit must last for ≥ 12 weeks to qualify as a response)
CR	
Bone marrow¹: Age-adjusted normocellularity; < 5% blasts; \leq Grade 1 MF² and
 
Peripheral blood: Hemoglobin ≥ 100 g/L and < ULN; neutrophil count $\geq 1 \times 10^9$/L and < ULN; Platelet count $\geq 100 \times 10^9$/L and < ULN; < 2% immature myeloid cells³ and
 
Clinical: Resolution of disease symptoms; spleen and liver not palpable; no evidence of EMH

PR	
Peripheral blood: Hemoglobin ≥ 100 g/L and < ULN; neutrophil count $\geq 1 \times 10^9$/L and < ULN;
 
Platelet count $\geq 100 \times 10^9$/L and < ULN; < 2% immature myeloid cells³ and
 
Clinical: Resolution of disease symptoms; spleen and liver not palpable; no evidence of EMH
 
or
 
Bone marrow¹: Age-adjusted normocellularity; < 5% blasts; \leq Grade 1 MF² and
 
Peripheral blood: Hemoglobin ≥ 85 g/L but < 100 g/L and < ULN; neutrophil count $\geq 1 \times 10^9$/L and < ULN; platelet count $\geq 50 \times 10^9$/L but < 100×10^9/L and < ULN; < 2% immature myeloid cells³ and
 
Clinical: Resolution of disease symptoms; spleen and liver not palpable; no evidence of EMH

Clinical improvement (CI)	The achievement of anemia, spleen or symptom response without progressive disease or increase in severity of anemia, thrombocytopenia or neutropenia ⁴
Anemia response	
Transfusion independent patients: a ≥ 20 g/L increase in hemoglobin level⁵
 
Transfusion dependent patients: becoming transfusion independent⁶

Spleen response⁷	
A baseline splenomegaly that is palpable 5-10cm below the LCM, becomes not palpable⁸
 
or
 
A baseline splenomegaly that is palpable > 10cm below the LCM, decreases by $\geq 50\%$⁸
 
A baseline splenomegaly that is palpable < 5cm below the LCM is not eligible for spleen response
 
A spleen response requires confirmation by MRI or CT showing $\geq 35\%$ spleen volume reduction

Symptom response	A $\geq 50\%$ reduction in the MPN-SAF TSS ⁹

Response categories	Required criteria (for all response categories, benefit must last for ≥ 12 weeks to qualify as a response)

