Progressive disease¹⁰	
Appearance of new splenomegaly that is palpable at least 5cm below the LCM or
 
$A \geq 100\%$ increase in palpable distance, below LCM, for baseline splenomegaly of 5-10 cm or
 
A 50% increase in palpable distance, below LCM, for baseline splenomegaly of > 10 cm or
 
Leukemic transformation confirmed by a bone marrow blast count of $\geq 20\%$ or
 
A peripheral blast content of $\geq 20\%$ associated with an absolute blast count of $\geq 1 \times 10^9/L$ that lasts for at least 2 weeks

Stable disease	Belonging to none of the above listed response categories
Relapse	
No longer meeting criteria for at least CI after achieving CR, PR or CI, or
 
Loss of anemia response persisting for at least 1 month or
 
Loss of spleen response persisting for at least 1 month

Cytogenetic remission	
At least 10 metaphases must be analyzed for cytogenetic response evaluation and requires confirmation by repeat testing within a 6-month window
 
CR: eradication of a preexisting abnormality
 
PR: $\geq 50\%$ reduction in abnormal metaphases (partial response applies only to patients with at least 10 abnormal metaphases at baseline)

Molecular remission	
Molecular response evaluation must be analyzed in peripheral blood granulocytes and requires confirmation by repeat testing within a 6-month window
 
CR: eradication of a preexisting abnormality
 
PR: $\geq 50\%$ decrease in allele burden (partial response applies only to patients with at least 20% mutant allele burden at baseline)

Cytogenetic/molecular relapse	Re-emergence of a pre-existing cytogenetic or molecular abnormality that is confirmed by repeat testing

Adapted from Tefferi, et al. Blood 2013; 122(8):1395-98.

EMH: extramedullary hematopoiesis (no evidence of EMH implies the absence of pathology- or imaging study-proven nonhematosplenic EMH). LCH: left costal margin. ULN: upper limit of normal.

1 Baseline and posttreatment bone marrow slides are to be interpreted at one sitting by a central review process. Cytogenetic and molecular responses are not required for CR assignment.

2 Grading of MF is according to the European classification. Thiele et al. European consensus on grading bone marrow fibrosis and assessment of cellularity. Haematologica 2005; 90: 1128.

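### Best-response rows leave no place for categories that bar stable disease, CMML marrow and cytogenetic responses have no specified count, and two MF response rules are misdirected

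*SAP*

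**What the plan says.** SAP 4.3.1 summarises best overall response by the disease-specific criteria of SAP Section 8, in five rows: "CR, PR, stable disease (SD), progressive disease (PD) or who are not evaluable (NE) as their best response on study".

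For Stage 3A the sponsor added stable disease to the 2015 MDS/MPN criteria as "a SD category, defined as those patients not belonging to any of the defined categories in the 2015 criteria" (SAP 1.1.3.3). Protocol Appendix 18.1 says the same: "those patients not belonging to any of the defined categories in the 2015 criteria has been added as response criteria for CMML patients". Those criteria (SAP Table 8-4) define CR, complete cytogenetic remission, partial remission, marrow response and clinical benefit.

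For MF, SAP Table 8-1 defines stable disease as "Belonging to none of the above listed response categories". Above it stand CR, PR, clinical improvement, anemia, spleen and symptom response, and progressive disease. Clinical improvement is "The achievement of anemia, spleen or symptom response without progressive disease or increase in severity of anemia, thrombocytopenia or neutropenia".

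Beyond ORR and best response, SAP 4.3.1 counts five CMML components: erythroid, platelet, neutrophil, spleen and symptom. For MF it counts clinical improvement, the anemia, spleen and symptom responses, molecular remission, and cytogenetic/molecular relapse. SAP 4.3.2 then gives a median duration to each MF category, ending with "molecular remission, or cytogenetic/molecular relapse, will be derived similar to the duration of objective response". Table 8-1 defines that relapse as "Re-emergence of a pre-existing cytogenetic or molecular abnormality that is confirmed by repeat testing". The MF paragraph of 4.3.1 times response to "the date from when each response of clinical benefit criteria (as defined in Table 8-4", which is the CMML table.

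**The concern.** There are three separate problems.

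(a) A best-response table should give every evaluable patient one row. Here, patients between PR and SD meet a definition that bars them from SD but have no row of their own. Whoever builds the table must either break the SD definition or apply a rule the SAP does not state. The sponsor added SD to remove uncertainty about classification, and this table brings some of it back.

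(b) Protocol Sections 1 and 2 say the endpoints of the 2015 criteria will each be evaluated in Stage 3A. Protocol 14.5 includes specific response components among the efficacy assessments. SAP 3.7 calls evaluation of individual 2015 components the single primary efficacy endpoint of Stage 3A. Marrow and cytogenetic response are among those categories, yet no SAP section specifies a count or interval for them. Stage 2 CMML bone marrow CR, which the protocol reports prominently, has none either.

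(c) In MF, a duration of response is assigned to an event that is a loss of response, and time to response is tied to another disease's criteria.

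**Working it through.** The plan gives no figure to reproduce for this point. The check sets definitions against planned tables.

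**1. Rows against definitions.** Take an evaluable Stage 3A patient whose only finding is a marrow response, with no progression.

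- CR: no, because peripheral counts have not normalised.
- PR: no, for the same reason.
- PD: no, by assumption.
- SD: no, because marrow response is a defined 2015 category.
- NE: the SAP does not define it, but the patient was assessed, so neither NE nor the missing-data category of SAP 3.10 fits.

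A patient with only complete cytogenetic remission fares the same. So does one with only clinical benefit, which by definition excludes CR, PR and progression. In MF the same holds for clinical improvement, and for an anemia, spleen or symptom response that fails to qualify as clinical improvement because a cytopenia worsened.

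Two groups are outside the gap. MF cytogenetic and molecular remission stand below SD in Table 8-1 and so do not bar it. Stage 2 CMML uses Table 8-3, where SD means PR not reached and no progression for more than 8 weeks; that can absorb a bone marrow CR.

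As an illustration, assume x such patients in a planned 20-patient cohort. If they are left out, the rows sum to (20 − x)/20: 95% for x = 1, 90% for x = 2, 80% for x = 4, 60% for x = 8. The documents do not give x.

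**2. Categories with no count.** The five CMML components in SAP 4.3.1 are those of clinical benefit. Stage 3A marrow response (optimal or partial) and complete cytogenetic remission, and Stage 2 bone marrow CR and cytogenetic response, have no count in any SAP section. The protocol's own figure, 4 of 36, is 4/36 = 11.1%, with an exact 95% interval of 3.1% to 26.1%. The SAP provides no such summary for this category.

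**3. Are the blast counts in SAP 4.3.8.1 a substitute?** They count, separately and at any time, a fall of at least 50% and a value below 5%, only in CMML patients with baseline marrow blasts of at least 5%. Bone marrow CR in Table 8-3 needs blasts of at most 5% together with a fall of at least 50%, lasting 4 weeks, with no baseline floor. Fall = (baseline − follow-up)/baseline.

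| Blasts | Fall | Table 8-3 blast criteria | Counted as ≥50% fall | Counted as <5% |
|---|---|---|---|---|
| 4% to 2% | (4−2)/4 = 50% | met | no, baseline below 5% | no, baseline below 5% |
| 10% to 5% | (10−5)/10 = 50% | met | yes | no |
| 6% to 4% | (6−4)/6 = 33% | not met | no | yes |
| 18% to 8% | (18−8)/18 = 56% | not met | yes | no |

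The first two rows are qualifying patients whom one or both counts miss; the last two are non-qualifying patients whom one count includes. Baseline marrow blasts below 5% are possible, since the CMML-1 definition in protocol 4.1.1 and 7.1.1 can be met on blood blasts of 2-4%. For Stage 3A the blast counts also ignore maturation, cellularity and fibrosis, which Table 8-4 uses for marrow response.

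**4. MF rules.** Relapse ends a remission, so a duration of response that starts at relapse has no meaning. Cytogenetic remission, which is defined in Table 8-1, appears in neither the 4.3.1 nor the 4.3.2 list. Table 8-4 verifies clinical benefit at 8 weeks, whereas Table 8-1 requires benefit for at least 12 weeks. SAP 1.2.5.1 takes the MF components from the IWG-MRT/ELN criteria, that is, Table 8-1. The pointer to Table 8-4 would therefore date MF responses by different criteria.

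**The case against.** Response is assessed by the investigator, and neither the eCRF coding nor the table shells (a separate document, per SAP Section 9) were available, so the missing rows may exist there. SAP 4.3.2 treats SD after CR or PR as a fall below CR/PR, which suggests a simple working hierarchy. One sentence defining SD for this table would close the gap without new rows. This stands as a choice of remedy, and it is why the finding is limited to the SAP text. The text itself still contradicts its own SD definitions.

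On the missing counts, protocol 14.5 names no marrow or cytogenetic category and leaves details to the SAP. SAP 1.1.3.3 and 1.2.5.1 name only the five clinical-benefit components for CMML, and by-patient listings cover all efficacy endpoints. It is therefore open to argument whether anything was dropped. But a listing is not a summary, and the protocol's undertaking to evaluate the 2015 endpoints individually is broader than the five components.

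The MF slips are fairly called editorial. The 4.3.2 list is introduced as inclusive, so it does not strictly exclude cytogenetic remission, and the Table 8-4 pointer may belong to the neighbouring CMML paragraph. They still need correcting, because followed literally they give wrong summaries.

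**Conclusion.** The point holds as a mismatch within the SAP text. Severity is minor to moderate, and the uncounted CMML marrow and cytogenetic responses are the most substantive part. ORR, the clinical-benefit component counts, MF clinical improvement (counted elsewhere in 4.3.1) and the Stage 3A activity criteria of SAP 3.1.2 are unaffected. SAP Section 5 leaves only descriptive analyses.

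A reader might go further in three ways that the documents do not support.

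- That a large share of responders is lost. Counting definitions without a row says nothing about patients, the MF categories overlap, and the number affected cannot be computed.
- That the 4 of 36 bone marrow CRs measure the gap. Their stage and SD status are not given, and Stage 2 SD can absorb them.
- That loss of remission will be reported as lasting benefit. The text shows a wording error, not an intention.

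The conclusion assumes that the unseen shells and eCRF coding do not already resolve these points. If they do, the SAP should say so.

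**What to change.** 1. In SAP 4.3.1, choose one of two routes. Either add best-response rows between PR and SD for the categories above, assigned by the best assessment on study, with absence of PD judged at that assessment and not over the whole study; otherwise a marrow response at C1 followed by PD at C4 would be recorded as PD. Or state that, in this table only, SD means no CR or PR and no PD. Say also whether partial cytogenetic response (Table 8-4, footnote 4) bars SD.
2. Add counts with exact intervals. Stage 3A: optimal and partial marrow response, complete and partial cytogenetic response, and any clinical benefit. Stage 2 CMML: bone marrow CR and cytogenetic response. These should be non-hierarchical, since Table 8-4 makes clinical benefit independent of marrow response and a patient may count in more than one.
3. In SAP 4.3.2, replace cytogenetic/molecular relapse with cytogenetic remission, and use relapse as the event that ends a cytogenetic or molecular remission. Add MF cytogenetic remission to 4.3.1.
4. Point MF time to response to Table 8-1.

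The cost is SAP wording, a few table rows and matching shell changes. Marrow and cytogenetic data are already scheduled at the end of C1 and C4 and then every 12 weeks. SAP 3.5 already separates Stages 1-2 from Stage 3A for CMML response, so the two sets of criteria need not be mixed. ORR does not change.
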